The change from Baseline in overall and each domain score of EORTC QLQ-C30 and GI.NET21 at each study visit will be analyzed using a MMRM for the PP population. The model will use the change from Baseline in overall or each domain score of EORTC QLQ-C30/GI.NET21 as the dependent variable and will include a fixed effect of time (Baseline Day 1 up to Week 84/EOS). The Baseline QLQ-C30/GI.NET21 value will be included in the model as a covariate. The Kenward-Roger approximation will be used to adjust the denominator degrees of freedom. A first-order heterogeneous autoregressive covariance structure will be assumed initially to model the within-patient errors; however, other covariance structures will be tested and may be used in the final model if a better fit is evident. The least squares (LS) means, 95% 2-sided CLs, and the p-values of LS means at each visit will be reported to evaluate the within-patient treatment effect. The null hypothesis is that there is no treatment effect (no difference from Baseline values) over time. A sample SAS code for the model is shown below.

*USUBJID: unique patient ID
AVISITN: analysis visit (e.g., week 24, week48, week 72 and week 84)
RESP: non-count data (e.g., change from Baseline in Global health status/QOL score)
BASE: non-count data (e.g., Baseline Global health status/QOL score);

```
ods output lsmeans=estimates;  
proc mixed data=adeft method=reml;  
  class USUBJID AVISITN;  
  model RESP = AVISITN BASE / ddfm=kr;  
  repeated AVISITN / subject=USUBJID type=ARH(1);  
  random intercept / subject=USUBJID;  
  lsmeans TRT01PN*AVISITN / cl;  
run;  
ods output close;
```

Friedman's nonparametric method for testing treatment group differences will be used to supplement the MMRM. Friedman's test uses the ranks of the data rather than their raw values to calculate the statistic, and the test does not make a distribution assumption of the data. The null hypothesis of the test is that the change from Baseline in Global health status/QOL score are the same over time, and the alternative hypothesis is that the change from Baseline in Global health status/QOL score are different over time. Friedman's test cannot handle missing data, so patients with incomplete measurements will be dropped when applying Friedman's test. A sample SAS code for the model is shown below.

*USUBJID: unique patient ID
AVISITN: analysis visit (eg, week 24, week48, week 72 and week 84)
RESP: change from Baseline in Global health status/QOL score;

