```
proc freq data=adeft;
```

Lexicon Pharmaceuticals, Inc.
[name]
[name]

1003157

Lexicon Pharmaceuticals, Inc.

LX1606.302

Final V1.0

Statistical Analysis Plan

```
tables USUBJID*AVISITN*RESP / cmh2 scores=rank noprint;  
output out = FriedRes (keep=group p_cmhrms) cmh2;  
run;
```

A graphic display of the change from Baseline value and its 95% CLs over time for each treatment group will be provided.

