8.6.3 Change from Baseline in Plasma Levels of 5-HIAA at Each Study Visit

Fasting (of at least 6 hours) blood samples, for measurement of 5-HIAA in plasma, will be collected and analyzed by a specialty laboratory based on the scheduled of visits in [Table 1](#).

The change from Baseline in plasma 5-HIAA levels will be analyzed using a MMRM. The model will use the change from Baseline in plasma 5-HIAA levels as the dependent variable, and will include patient as a random effect, Baseline plasma 5-HIAA levels as a covariate, time as fixed effect. The Kenward-Roger approximation will be used to adjust the denominator degrees of freedom. A first-order heterogeneous autoregressive covariance structure will be assumed initially to model the within-patient errors; however, other covariance structures will be tested and may be used in the final model if a better fit is evident. The LS means, a 95% 2-sided CLs and the p-values of LS means at each visit will be reported for each study visit to evaluate the treatment effect. A sample SAS code for the model is shown below.

*USUBJID: unique patient ID
AVISITN: analysis visit (eg, week 12, 24, 36, 48, 60, 72, 84 and follow-up visit)
PLA5HIAA: Baseline plasma 5-HIAA levels
RESP: non-count data (eg, change from Baseline in plasma 5-HIAA level)

```
ods output lsmeans=estimates;  
proc mixed data=adev method=reml;  
  class USUBJID AVISITN;  
  model RESP = PLA5HIAA AVISITN / ddfm=kr;  
  repeated AVISITN / subject=USUBJID type=ARH(1);  
  random intercept / subject=USUBJID;  
  lsmeans TRT01PN*AVISITN / cl;  
run;  
ods output close;
```

Lexicon Pharmaceuticals, Inc.
[name]
[name]

1003157

Lexicon Pharmaceuticals, Inc.

LX1606.302

Final V1.0

Statistical Analysis Plan

Descriptive summary statistics will be provided for the observed value and change from Baseline value of the plasma 5-HIAA levels. A graphic display of the parameter estimates and the 95% CLs for the plasma 5-HIAA levels over time will be provided.

Friedman's test for repeated measures will be used to supplement the MMRM, which is similar to that applied in Section **Error! Reference source not found.****Error! Reference source not found.**

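### The supplementary Friedman test in SAP Section 8.6.1 compares post-Baseline visits with each other, so it cannot corroborate or challenge the MMRM's test of change from Baseline

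*SAP*

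**What the plan says.** Section 8.6 has the tests and estimates of within-patient effects come from the MMRM, with non-parametric methods as a supplement. Section 8.6.1 then describes two tests with different hypotheses.

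- **MMRM null:** "The null hypothesis is that there is no treatment effect (no difference from Baseline values) over time".
- **Purpose given for Friedman's test:** "Friedman's nonparametric method for testing treatment group differences will be used to supplement the MMRM".
- **Friedman null:** "The null hypothesis of the test is that the change from Baseline in Global health status/QOL score are the same over time".
- **Friedman code:** "tables USUBJID*AVISITN*RESP / cmh2 scores=rank noprint". The strata are patients, the rows are visits and the response is change from Baseline. The visit list above this code names Weeks 24, 48, 72 and 84, as does the list above the MMRM code ("AVISITN: analysis visit (e.g., week 24, week48, week 72 and week 84"). Baseline is in neither list.
- **Incomplete patients:** "Friedman's test cannot handle missing data, so patients with incomplete measurements will be dropped when applying Friedman's test". Section 7.3 plans no imputation.

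For plasma 5-HIAA, Section 8.6.3 prints a visit list above the MMRM code: "AVISITN: analysis visit (eg, week 12, 24, 36, 48, 60, 72, 84 and follow-up visit". It then calls for a similar Friedman test through a cross-reference that failed to resolve, and gives no separate visit list for that test. Section 4.1 describes the Follow-up Period as 14 days without study drug.

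**The concern.** A supplementary non-parametric test is useful when it asks the same question as the model under weaker assumptions. Here the model asks whether scores moved from Baseline, and the rank test asks whether the movement was the same at every visit. A large, sustained change would give a small MMRM p-value and an unremarkable Friedman p-value. A drift between visits could do the reverse. A reader of the report would take the first pattern as a failed robustness check and the second as confirmation, and both conclusions would be unfounded.

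Two further points affect what the p-value means. The text and the code disagree on which patients contribute. For 5-HIAA it is open whether an off-drug measurement is one of the visits compared.

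**Working it through.** The SAP gives no power or sample size figure for this test, so there is no stated number to reproduce. It also gives no SD, correlation, effect size or dropout rate. The values below are assumptions for illustration. Step 1 needs none of them.

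**1. Baseline cancels.** For patient *i* with Baseline *b_i* and visit scores *y_i1, …, y_i4*, the response is *c_ij = y_ij − b_i*. Within a patient, *c_ij < c_ik* exactly when *y_ij < y_ik*, so the ranks of the changes equal the ranks of the raw post-Baseline scores. In one simulated data set Friedman's p-value was 0.5164 on the changes and 0.5164 on the raw scores. Adding any constant to all of a patient's post-Baseline scores also leaves the statistic unchanged.

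**2. Power against a sustained change.** Assumptions: equal correlation of 0.5 between all time points, SD 1 at each, 4 post-Baseline visits, no missing data, 2-sided 0.05, 2,000 runs per setting. The SD of a change is √(2 × (1 − 0.5)) = 1, so a shift of 0.5 SD is also 0.5 SD of the change. Rejection rates for the same 0.5 SD change at all four visits:

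| n | Friedman as planned | Signed-rank, one visit | Friedman with Baseline as a level |
|---|---|---|---|
| 30 | 5.0% | 73% | 66% |
| 60 | 5.2% | 97% | 96% |
| 100 | 5.1% | 99.9% | 99.8% |

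At 1.0 SD the planned test still rejects in only 4.3% to 4.8% of runs. Repeat runs gave 76% for signed-rank at n = 30, hence about 75% as a round figure.

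**3. Complete cases.** Patients left of 100 = 100 × (1 − d) × (1 − m)^K, where d is discontinuation, m is missingness per visit, and K is 4 for QoL or 8 for 5-HIAA with Follow-up.

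| d, m | K = 4 | K = 8 |
|---|---|---|
| 20%, 5% | 100 × 0.80 × 0.95^4 = 65 | 100 × 0.80 × 0.95^8 = 53 |
| 40%, 5% | 49 | 40 |
| 60%, 10% | 26 | 17 |

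Two features of the plan add to this loss. The note to file of November 23, 2015 moves early discontinuers' EOS data to the analysis visit that matches their study day, so their later visits stay empty. The first report uses a data cut-off (Section 2.2), so patients still in the study are incomplete.

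**4. Text against code.** With complete data the printed stratified row-mean-score statistic equals Friedman's (4.88 by both routes in one example). With missing visits it still uses any patient who has at least two. In a simulated example of 60 patients with dropout, the code used 54 (statistic 3.95, p = 0.27), and the text's rule left 40 (2.73, p = 0.44).

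**5. Follow-up in the 5-HIAA test, if included.** With on-drug values flat and an assumed 0.5 SD rise at Follow-up only, Friedman over 8 visits rejects in 64% of runs at n = 30, 95% at n = 60 and 99.8% at n = 100. Repeat runs gave 63% and 93% at the first two sizes. Without Follow-up the rate is about 5%.

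**The case against.** The strongest defence is that Section 8.6.1 states Friedman's null openly and the code matches it. Baseline is itself on drug, because patients continue without interruption, so whether changes drift between visits is a fair question in a long-term extension. To supplement a model need not mean retesting the same null, and a constant shift is the scenario least favourable to Friedman. The drift question is indeed legitimate. However, the SAP does not present the test as a drift test. It presents it as a test of treatment groups that supplements a model whose null concerns Baseline, and whatever part of a change is common to all visits stays invisible to it.

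The visit lists are marked as examples, and the MMRM text speaks of time from Baseline Day 1, so Baseline might be added as a level. That would work, as step 2 shows, but neither the Friedman visit list nor its null includes Baseline.

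A reader might infer that the 5-HIAA Friedman test will include the off-drug visit. The documents do not establish this. The list with Follow-up is an example printed above the MMRM code, and the Friedman test is reached only through a broken reference. The supportable statement is that nothing excludes Follow-up. Nor does wash-out guarantee significance: under the assumed rise, about a third of runs at n = 30 do not reach it.

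A reader might also infer that only complete patients will be analysed. That is the text's rule, but the printed code follows it only if the data are filtered first.

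**Conclusion.** The point stands. The description as a test of treatment groups is wrong for this code. The test is blind to any change from Baseline that is the same at every visit. That follows from algebra and rests on no assumption. The rejection rates (about 5% against about 75% to 99.9% for a constant 0.5 SD change) depend on the assumed correlation and sample sizes, and the retention counts on assumed losses. The text-code conflict over incomplete patients is certain, but its effect on any p-value depends on the data. The Follow-up issue is an ambiguity to close.

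The consequence is modest. Safety is the primary objective (Section 3.1), no formal sample size calculation was made (Section 4.5), the study is open-label and not randomised (Section 4.6), and the MMRM carries the efficacy estimates. A reader might infer that the efficacy conclusions themselves are compromised. The documents do not support that, because only the supplementary p-values are affected.

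**What to change.** Replace Friedman's test with a Wilcoxon signed-rank test of zero change at each on-treatment visit, with a Hodges-Lehmann estimate and 95% CI. Use all patients with data at that visit, in the same population as the MMRM. That population must first be settled: Sections 6 and 6.2 name the SAF for the primary efficacy analyses, while Sections 8.6 and 8.6.1 run them on the PP population. Report Follow-up separately as off-drug, delete the phrase about treatment groups and repair the cross-reference in Section 8.6.3.

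If Friedman's test is kept, there are two options: describe it only as a test of differences between visits, or include Baseline as a level using raw scores. In either case, say whether Follow-up is a level and make the code apply the complete-case rule.

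The cost is SAP wording and simple code, plus more unadjusted p-values. If the test is applied to every scale and item in Tables 2 and 3 (15 + 9 = 24), four visits give 24 × 4 = 96 p-values in place of 24. They should be labelled descriptive. The MMRM already reports one p-value per visit, so the layout of the two analyses would then match.

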8.6.2 Subjective Global Assessment

8.6.2.1 Proportion of Patients that Report Adequate Relief of CS Symptoms at Each Study Visit

At each study visit, patients will be asked to respond to the following question: “In the past 7 days, have you had adequate relief of your carcinoid syndrome bowel complaints such as diarrhea, urgent need to have a bowel movement, abdominal pain, or discomfort?” Patients are regarded as reporting adequate relief of CS symptoms during the previous week if the result to the question answered is “yes”.

The number of patients that report adequate relief of CS symptoms and its percentage along with the corresponding exact 95% CIs will be summarized by study visit.

Generalized linear mixed model can be used to fit the binary response with repeated measurements. The odds ratio of each telotristat etiprate group versus its Baseline, its associated 95% CI and p-value will be reported for each post-Baseline visit. A sample SAS code for the model is shown below:

```
*USUBJID: unique patient ID  
AVISITN: analysis visit (eg, week 12, 24, 36, 48, 60, 72, 84 and Follow-up)  
RESP: binary response data (eg, ‘Yes’ for adequate relief of CS symptoms)  
BASE: Baseline response;  
  
proc glimmix data=adef;  
class USUBJID AVISITN PLA5HIAA;  
model RESP = AVISITN BASE /  
solution dist=binomial link=logit ddfm=kr oddsratio;  
random intercept / subject=USUBJID ;  
random AVISITN / subject=USUBJID type=ARH(1);  
run;
```

A graph of the percentage of patients that report adequate relief of CS symptoms by study visit and treatment group will be plotted.

1003157

Lexicon Pharmaceuticals, Inc.

LX1606.302

Final V1.0

Statistical Analysis Plan

8.6.2.2 Change from Baseline in subjective global assessment of CS symptoms on an 11-point NRS at each study visit

Patients will be asked the following question at each study visit to assess global symptoms associated with CS on an 11-point scale: “Rate the severity of your overall carcinoid syndrome symptoms over the past 7 days on a scale from 0-10, where 0=no symptoms and 10 = worst symptoms ever experienced.”

Analysis of this endpoint is similar to that applied in [Section 8.6.1 Change from Baseline in Overall and Domain Scores of the EORTC QLQ-C30 and GI.NET21 at Each Study Visit](#). A graphic display of the change from Baseline value and its 95% CLs over time for each treatment group will be provided.

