7 GENERAL ASPECTS FOR STATISTICAL ANALYSIS

7.1 GENERAL METHODS

Statistical methodology and analyses are in accordance with the principles outlined by the International Conference on Harmonisation (ICH) E9 guidelines^[1].

Patient listings of all data represented in the electronic case report form (eCRF) will be provided. Measurements from patients excluded from the predefined analysis populations or extra measurements (such as unscheduled or repeat assessments) will not be included in summary tables unless specified otherwise, but will be included in the patient listings. In general, the patient listings will be sorted by treatment group,

1003157

Lexicon Pharmaceuticals, Inc.

LX1606.302

Final V1.0

Statistical Analysis Plan

patient number, and assessment date (and time), if applicable. For most summary statistics, data will be analyzed and displayed by the order of the treatment groups and overall, where treatment groups correspond to how patients were dosed on Day 1 of this study.

Unless otherwise specified, continuous/quantitative variables will be summarized using descriptive statistics, which will include the number of patients with data to be summarized (n), mean, standard deviation (SD), median, minimum, and maximum. The same number of decimal places as in the raw data will be presented when reporting the minimum and maximum, 1 more decimal place than in the raw data will be presented when reporting the mean and median, and 2 more decimal places than in the raw data will be presented when reporting the SD.

All categorical/qualitative data will be presented using frequency counts and percentages. The total number of patients in the treatment group overall (N) will be used as the denominator for percentage calculations, unless stated otherwise in the table shell. All percentages will be presented as 1 decimal point, unless otherwise specified. Percentages equal to 100 will be presented as 100%, and percentages will not be presented for zero frequencies.

All statistical tests will be 2-sided and have an associated α -level = 0.05 unless mentioned otherwise. Confidence limits (CLs) will be 2-sided and calculated with a 95% confidence coefficient.

All statistical analyses will be done using SAS statistical software version 9.3 or higher.

In the case of multiple or repeat assessments at a scheduled visit, the latest value at the visit will be used for summarization and analyses.

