14.2.5.2 Table Conventions

- Units will be included where available
- If the categories of a parameter are ordered, then all categories between the maximum and minimum category should be presented in the table, even if $n = 0$ for all treatment groups in a given category that is between the minimum and maximum level for that parameter. For example, the frequency distribution for symptom severity would appear as:

Severity Rating	N
severe	0
moderate	8
mild	3

Where percentages are presented in these tables, 0 percentage will not be presented and so any counts of 0 will be presented as 0 and not as 0 (0%).

- If the categories are not ordered (e.g., Medical History, etc.), then only those categories for which there is at least 1 patient represented in 1 or more groups should be included.
- An Unknown or Missing category should be added to any parameter for which information is not available for 1 or more patients.
- Unless otherwise specified, the estimated mean and median for a set of values should be printed out to 1 more significant digit than the original values, and standard deviations should be printed out to 2 more significant digits than the original values. The minimum and maximum should report the same significant digits as the original values. For example, for systolic blood pressure:

N	XX
Mean	XXX.X

1003157

Lexicon Pharmaceuticals, Inc.

LX1606.302

Final V1.0

Statistical Analysis Plan

SD	X.XX
Median	XXX.X
Min, Max	XXX, XXX

- Percentage values should be printed to 1 decimal place, in parentheses with no spaces, 1 space after the count (e.g., 7 (12.8), 13 (5.4)). Predetermine how to display values that round down to 0.0. A common convention is to display as '< 0.1', or as appropriate with additional decimal places. Unless otherwise noted, for all percentages, the number of patients in the analysis set for the treatment group who have an observation will be the denominator. Percentages after 0 counts should not be displayed and percentages equating to 100% should be presented as 100, without any decimal places.

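### The adequate-relief model in SAP 8.6.2.1 cannot yield the promised odds ratio versus Baseline by dose group, and the SAP has two conflicting default denominators for by-visit percentages

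*SAP*

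**What the plan says.** Section 8.6.2.1 asks each patient a yes/no question at each visit and plans two results. The first is the number and percentage with adequate relief, with an exact 95% interval, by visit. The second is inferential: "The odds ratio of each telotristat etiprate group versus its Baseline, its associated 95% CI and p-value will be reported for each post-Baseline visit".

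The prose says only that a generalized linear mixed model can be used, so the sample code is the only place where model terms are named:

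- Visit factor: "AVISITN: analysis visit (eg, week 12, 24, 36, 48, 60, 72, 84 and Follow-up".
- Baseline: "BASE: Baseline response".
- Fixed effects: "model RESP = AVISITN BASE", with no dose-group variable.
- The CLASS statement also lists PLA5HIAA, which Section 8.6.3 defines as Baseline plasma 5-HIAA. It does not appear in this model.

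Section 8.6.2.1 gives no denominator for the percentage. Section 7.1 says: "The total number of patients in the treatment group overall (N) will be used as the denominator for percentage calculations", with an exception where a table shell says otherwise. The programming conventions in Section 14 likewise use the analysis population and treatment group. Section 14.2.5.2 sets a different default: "the number of patients in the analysis set for the treatment group who have an observation will be the denominator". A later bullet in the same section refers to patients assessed. Section 7.3 rules out imputation.

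**The concern.** A contrast with Baseline needs Baseline responses among the modelled outcomes. Here the Baseline answer appears only on the right-hand side, so the model describes relief at later visits given the Baseline answer. It says nothing about how often relief was reported at Baseline. For the continuous endpoints the same layout works, because the outcome in Section 8.6.1 is already a change score and zero means no change. A yes/no answer has no such change score, so the layout does not carry over.

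Adequate relief is one of three efficacy endpoints in Section 5.1, and this odds ratio is its only planned inferential result. A programmer must either depart from the code or put some other odds ratio under the promised title.

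The denominator matters because patients leave an 84-week extension and missing answers are not imputed. Dividing by all patients makes the percentage fall with dropout even when relief among those still assessed is constant. The same conflict reaches other by-visit percentages, such as the QTcF outliers in Section 9.5 and the abnormal examinations in Section 9.6.

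**Working it through.** The SAP states no odds ratio or expected relief rate, so there is no planned figure to reproduce. The relief rates and numbers assessed below are assumptions.

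**1. Is the contrast estimable?** From the sample code, the fixed-effect columns are an intercept, 8 visit indicators (Weeks 12, 24, 36, 48, 60, 72, 84 and Follow-up) and BASE. The visit indicators sum to the intercept, so the rank is 1 + 8 + 1 − 1 = 9. A contrast of visit minus Baseline needs a Baseline column, which is zero in every row. Adding the contrast as a row raises the rank to 10. It lies outside the row space, so it is not estimable. The model can give odds ratios among the 8 listed visits and one odds ratio for BASE.

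**2. What this means in numbers.** Assume relief at a later visit is 0.40 if the Baseline answer was no and 0.70 if it was yes. The BASE odds ratio is then (0.70/0.30)/(0.40/0.60) = 3.5. Keep these coefficients fixed and vary Baseline relief p. Relief at the visit is 0.40(1 − p) + 0.70p. Random effects are left out for illustration.

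| Baseline relief p | Relief at visit | Odds at visit / odds at Baseline | Odds ratio versus Baseline |
|---|---|---|---|
| 0.30 | 0.49 | 0.961 / 0.429 | 2.24 |
| 0.50 | 0.55 | 1.222 / 1.000 | 1.22 |
| 0.80 | 0.64 | 1.778 / 4.000 | 0.44 |

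The fitted model is identical in all three rows.

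**3. Does adding Baseline to the visit list repair it?** Not while BASE stays, because in the Baseline rows the response equals its own covariate. Fitting the logistic model to the expected counts from step 2:

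| Baseline relief | Correct odds ratio | Baseline added, BASE kept | Baseline added, BASE dropped |
|---|---|---|---|
| 0.30 | 2.24 | 2.53 | 2.24 |
| 0.50 | 1.22 | 1.27 | 1.22 |
| 0.80 | 0.44 | 0.41 | 0.44 |

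**4. By dose group.** With no dose term and no dose-by-visit term, every group shares the same visit effects. No group-specific odds ratio can be formed, whatever is done about Baseline.

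**5. Denominators.** Assume 100 patients (the SAP's upper limit on enrolment), with exact (Clopper-Pearson) 95% intervals.

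| Assessed | 'Yes' | Divided by all 100 | Divided by assessed |
|---|---|---|---|
| 90 | 54 | 54.0% (43.7-64.0) | 60.0% (49.1-70.2) |
| 60 | 40 | 40.0% (30.3-50.3) | 66.7% (53.3-78.3) |
| 50 | 30 | 30.0% (21.2-40.0) | 60.0% (45.2-73.6) |

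In the first and third rows relief among those assessed is 60.0% both times, yet the all-patient figure falls from 54.0% to 30.0%.

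**The case against.** The code is labelled a sample, the visit list is given as examples, and the prose says only that such a model can be used. The study is an open-label, non-randomised extension whose primary objective is safety, with no formal sample size calculation. Percentages with exact intervals are reported separately. This limits the consequences, but it does not make the odds ratio obtainable: no other text names the model terms, and reading Baseline into the visit list fails by step 3.

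On denominators, the table shells may override the default, and they are not shown. Section 8.6 bases efficacy on observed data, which favours patients assessed. Both are fair and soften the point. The written defaults still differ, and Section 8.6.2.1 does not choose between them.

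On dose terms, the note of November 3, 2015 describes 500 mg tid for all open-label patients, while Section 4.1 and the note of November 23, 2015 have patients continue at their parent-study dose. These statements need to be reconciled. If one dose dominates, dose-by-visit terms may be too sparse to fit.

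Four stronger readings are tempting but not supported:

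- *The code would report on-drug visits against off-drug Follow-up, perhaps with the event inverted.* This depends on software defaults and variable coding that the SAP does not give.
- *A spurious odds ratio of a particular size would be printed.* An odds ratio computed from assumed raw proportions is marginal, while the coded model, with a patient random intercept, gives a conditional one.
- *The visit-level term "random AVISITN / subject=USUBJID type=ARH(1" cannot be identified.* This is not shown. Correlations across repeated visits carry information, so weak identification is the most that can be said.
- *The endpoint is mislabelled because the question asks "have you had adequate relief of your carcinoid syndrome bowel complaints such as diarrhea".* The section prints the question and defines the endpoint as a 'yes' to it, so renaming is a preference.

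**Conclusion.** The point holds in two parts. First, the odds ratio of each dose group versus its Baseline is not estimable from the only model the SAP specifies. The rank result (9 against 10) and the absence of a dose term follow from the listed terms alone and rest on no assumed data or software behaviour. The range 2.24 to 0.44 is illustrative and rests on the assumed relief rates. PLA5HIAA in CLASS is a stray.

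Second, the SAP has two incompatible default denominators. The example of 40.0% against 66.7% shows how far they can part at an assumed 60% assessed. The shells may settle this, but the text does not.

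This should be fixed. It affects one efficacy endpoint of a safety extension and leaves the primary safety objective untouched. A reader might infer that the tables would present a withdrawal effect as long-term benefit; the documents do not establish that.

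**What to change.** Revise Section 8.6.2.1 and its code as follows:

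- Include the Baseline answers as response rows, make Baseline a level of AVISITN, name it explicitly as the reference, and drop BASE.
- State explicitly that the modelled event is 'Yes'.
- Remove PLA5HIAA from CLASS.
- Report Follow-up separately and label it off-drug, since Section 4.1 gives no study drug in that period.
- Either add dose group and dose-by-visit terms or, if the doses are too sparse, state that only a pooled odds ratio versus Baseline is reported.

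Set one denominator rule for by-visit percentages and their exact intervals: patients assessed at that visit, with N shown alongside. Align Sections 7.1, 14 and 14.2.5.2 with it.

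The cost is a few lines of text and code. By-visit intervals become somewhat wider than those based on all patients: in the example with 60 assessed, 25.0 points (78.3 − 53.3) against 20.0 (50.3 − 30.3).
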